****I. Study Background:****

Restless Legs Syndrome (RLS) is a common complication in uremic patients, significantly impacting their quality of life and prognosis. Many studies have found that RLS is closely related to nocturnal hypertension and the occurrence of cardiovascular events in uremic patients, affects patient sleep, leads to anxiety, depression, and decreased quality of life. The mortality rate of hemodialysis (HD) patients with RLS is significantly higher than that of patients without RLS [1]. Over the past few decades, dopaminergic drugs have been the mainstay of first-line treatment for RLS. Although these drugs show significant short-term efficacy, long-term use is characterized by short half-life, susceptibility to early morning rebound, and poor long-term efficacy [2, 3]. Recent studies suggest that nucleoside equilibrative transporter inhibitors, such as dipyridamole and ticagrelor, may control RLS symptoms by increasing endogenous adenosine-mediated tonic A1 receptor activation, potentially representing a new treatment strategy for RLS [4, 5]. Preliminary clinical studies have demonstrated that dipyridamole significantly improves patients' sleep quality and quality of life [6].

We will only screen patients who meet both the inclusion and exclusion criteria to participate in this study. Enrolled patients will receive dipyridamole free of charge, 50 mg each time, three times a day, for a total of 12 weeks. During the treatment period, we will regularly follow up on

the participants' condition. Participants will need to undergo assessments using the International Restless Legs Syndrome Study Group Rating Scale (IRLS), Clinical Global Impression scale (CGI), Medical Outcomes Study Sleep Scale (MOS-SS), etc., before and after treatment to evaluate the degree of symptom change. Through this treatment, we aim to understand the specific efficacy of dipyridamole in uremic patients with RLS, the extent to which the drug improves RLS sensory and motor symptoms and sleep conditions, observe the impact of dipyridamole on concomitant depression, anxiety, quality of life, etc., in maintenance dialysis patients, and also understand the efficacy and common adverse reactions of dipyridamole in clinical use in maintenance dialysis patients.

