****2. Study Procedure:****

- (1) Screen patients undergoing maintenance hemodialysis at our hospital's dialysis center whose baseline International Restless Legs Syndrome Study Group Rating Scale (IRLS) score is >15 points.
- (2) Patients who meet the inclusion criteria and are willing to sign the informed consent form.
- (3) Collect general clinical data and pre-treatment laboratory parameters, including age, gender, body mass index, Charlson Comorbidity Index score, dialysis duration, serum iron, ferritin, serum parathyroid hormone, hemoglobin, albumin, and dialysis adequacy. Assess changes in patient condition before and after treatment using scales such as the International Restless Legs Syndrome Study Group Rating Scale (IRLS), Pittsburgh Sleep Quality Index (PSQI), Hamilton Depression Rating Scale (HAMD), Hamilton Anxiety Rating Scale (HAMA), Clinical Global Impression scale (CGI), Medical Outcomes Study Sleep Scale (MOS-SS), Epworth Sleepiness Scale (ESS), and KDQOL-SF™-36.
- (4) All enrolled RLS patients will be instructed by designated personnel to orally take dipyridamole tablets, 50mg each time, three times a day, for a continuous period of 12 weeks.
- (5) Collect information on the occurrence of drug-related adverse reactions during the study period, such as nausea, headache, dizziness, diarrhea, insomnia, fatigue, bleeding, etc. The follow-up period is 12 weeks.
- (6) After the treatment concludes, collect the patients' general clinical data and laboratory parameters again.
- (7) Statistical Analysis: Measurement data conforming to a normal distribution will be expressed as mean \pm standard deviation ($\bar{x} \pm s$). Count data will be expressed as frequencies. Comparisons of means before and after treatment will be performed using paired-sample t-tests. Comparisons of rates before and after treatment will be performed using paired-sample chi-square tests. A P-value < 0.05 will be considered statistically significant. All statistical analyses will be performed using SPSS software.
- (8) Evaluate changes in patient condition before and after treatment. Primary evaluation indicators: complete remission rate, partial remission rate, overall response rate, incidence of adverse events, dropout rate.

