****3. Sample Size Calculation:****

$$\text{Formula: } n = [(Z \alpha / 2 + Z \beta) * \sigma / \Delta]^2$$

Where n is the sample size, $Z \alpha / 2$ is the two-sided quantile of the normal distribution corresponding to the significance level α (usually $\alpha = 0.05$, so $Z \alpha / 2 = 1.96$). $Z \beta$ is the quantile

of the normal distribution corresponding to the power ($1 - \beta$) (power is usually set at 0.8, so $Z\beta = 0.84$). σ is the standard deviation of the observation indicator, reflecting data dispersion. Δ is the expected mean difference before and after treatment, i.e., the minimum difference expected to be detected. Based on literature review and preliminary studies, we set $\sigma = 4$ and $\Delta = 2$. Therefore, the calculated sample size $n = 31.36$. Rounding up, $n=32$. Considering potential dropouts, the sample size needs to be increased by 10%-20%, so the final sample size is set at 80.

4. Data Analysis and Statistical Methods:

Conduct statistical analysis on the obtained data: Measurement data conforming to a normal distribution will be expressed as mean \pm standard deviation ($\bar{x} \pm s$). Count data will be expressed as frequencies. Comparisons of means before and after treatment will be performed using paired-sample t-tests. Comparisons of rates before and after treatment will be performed using chi-square tests. A P-value < 0.05 will be considered statistically significant.

Study Flowchart:

Patient Screening

↓

Collection of Patient Clinical and Laboratory Data

↓

Oral Administration of Dipyridamole Tablets under Guidance

↓ (12 weeks)

Collection of Drug-Related Adverse Reactions during the Study

↓

Post-Treatment Collection of General Clinical Data and Laboratory Parameters

↓

Statistical Analysis, Efficacy Evaluation, Manuscript Preparation

5. Safety Analysis and Content Evaluation:

Follow up and statistics on the types, number of cases, and severity grading of potential adverse reactions during dipyridamole treatment. Evaluate the causes of these adverse reactions and their causal relationship with the study drug. Calculate the incidence of adverse reactions. Main adverse reactions may include headache, dizziness, gastrointestinal discomfort (nausea, vomiting, diarrhea), hypotension, bleeding tendency, allergic reactions, etc.

6. Observation Indicators:

Primary Indicators: Restless Legs Syndrome symptom severity score (IRLS).

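### Patients without a second IRLS drop out of the paired t-test, and the protocol does not provide for scoring those who stop the drug early, so the mean improvement may be overstated

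*Protocol*

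**What the plan says.** The analysis is given in the Protocol, III.2 Study Procedure, step (7): "Comparisons of means before and after treatment will be performed using paired-sample t-tests". III.4 repeats the test and opens with "Conduct statistical analysis on the obtained data". III.6 names the IRLS score as the primary indicator. III.2 step (8) lists remission and response rates, adverse events and the dropout rate as primary evaluation indicators.

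On timing, I and III.2 step (3) place the scales before and after treatment, and the flowchart puts the post-treatment data collection after 12 weeks of the drug. Section I adds "During the treatment period, we will regularly follow up on" the participants' condition, but no section attaches an IRLS to that follow-up.

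On dropout, III.3 says: "Considering potential dropouts, the sample size needs to be increased by 10%-20" per cent, and sets the final number at 80. VI (5) lets patients withdraw at any stage and offers them medical advice and an unburdened exit. It mentions no last assessment.

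**The concern.** A paired t-test needs two scores per patient. With one planned post-treatment IRLS, a patient who stops early and is not scored has only a baseline value and cannot enter the test. Enrolling more patients replaces the lost numbers but not the lost outcomes. If the unscored patients tend to do worse, the mean change among those scored is larger than the mean change among all who were started on the drug. There is no control arm in which similar losses could be seen and compared.

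The rules for analysis sets and missing data can reasonably wait for a statistical analysis plan. Whether an IRLS is obtained from a patient who has stopped the drug cannot, because it is a decision about data collection and has to be made before the visit passes.

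**Working it through.** **Inputs.** From III.3: Δ = 2, σ = 4, two-sided α = 0.05 (z = 1.96), power 0.80 (z = 0.84), dropout allowance 10% to 20%, final N = 80. The mean change *c* in patients without a second score is not in the protocol. It is an assumption and is varied below.

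**The plan's own figure.** n = [(1.96 + 0.84) × 4 / 2]² = 5.6² = 31.36, rounded up to 32. This reproduces. Allowing for dropout gives 32/0.9 = 35.6, so 36, or 32/0.8 = 40. The final 80 does not follow from these figures. That is a separate point, and it matters here only because it leaves ample power.

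**Is power at stake?** No. From 80 patients, 10% dropout leaves 72 and 20% leaves 64. The paired t-test for a change of 2 with SD 4 (noncentral t) then has power of 98.7% and 97.6%.

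**Is the estimate at stake?** Let *d* be the proportion without a second score and *m* the mean improvement among those scored. Then:

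- change in all enrolled = (1 − d) × m + d × c
- overstatement by the paired analysis = d × (m − c)

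With m = 2.0:

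| Assumed c | All enrolled, d = 10% | Overstatement | All enrolled, d = 20% | Overstatement |
|---|---|---|---|---|
| 2 (same improvement) | 2.0 | 0 | 2.0 | 0 |
| 1 | 1.9 | 0.1 | 1.8 | 0.2 |
| 0 (no change) | 1.8 | 0.2 | 1.6 | 0.4 |
| −2 (worse by 2) | 1.6 | 0.4 | 1.2 | 0.8 |
| 3 (better than those scored) | 2.1 | −0.1 | 2.2 | −0.2 |

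In the no-change row the overstatement is 2.0/1.8 − 1 = 11% or 2.0/1.6 − 1 = 25% of the all-enrolled change. In units of the planned SD it is 0.2/4 = 0.05 or 0.4/4 = 0.10.

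**Would the test result change?** Put all 80 in the analysis with zero change for the unscored. The variance is (1 − d)(σ² + m²) − [(1 − d)m]².

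- d = 10%: 0.9 × 20 − 1.8² = 14.76, SD 3.84, mean 1.8, power 98.5%.
- d = 20%: 0.8 × 20 − 1.6² = 13.44, SD 3.67, mean 1.6, power 97.1%.

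On the plan's assumptions the size of the effect moves and the significance test hardly does.

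**Rates.** If unscored patients are counted as non-responders, a rate among scored patients is multiplied by (1 − d), that is by 0.9 or 0.8. For example, an assumed 30% of 64 scored patients is 19.2, which is 24% of 80.

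**The case against.** A reader might infer that the plan analyses completers only, that it expects 10% to 20% of patients to stop because of side effects or lack of benefit, and that the effect is therefore inflated. The protocol supports none of these three statements.

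- It never restricts the test to patients who finish 12 weeks. A patient who stops the drug but is scored afterwards stays in the test. The scale assessments are not limited to finishers, and the 12-week follow-up is not tied to continued dosing. The protocol is silent on scoring after stopping; it does not rule it out.
- The 10% to 20% is a sample-size allowance for possible losses. It is not a forecast, and no reasons are attached.
- The direction of bias depends on outcomes that nobody has yet seen. The table contains a row with no bias and a row with understatement.

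Three more objections carry weight. Missing-data methods are commonly left to the analysis plan. Losses will be visible, because the dropout rate is itself reported. With no change in the unscored, the shift is at most 0.4 points and the test keeps its power.

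These objections limit the claim but do not remove it. Reporting the dropout rate shows how many were lost and does not correct the mean. An analysis plan can choose how to treat missing scores but cannot obtain them. In an uncontrolled study the size of the change is the main result, so a shift in it matters even when the P-value does not move.

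**Conclusion.** The point holds as a conditional one about data collection. As written, the paired comparison excludes every patient without a second IRLS, no section secures that score for patients who stop early, and the only provision for dropout is a larger sample. If the unscored patients do worse than those scored, the mean improvement is overstated. The overstatement is 0.2 points at 10% dropout and 0.4 points at 20%, against a planned change of 2, if they do not change at all. It is larger if they worsen and zero if they improve equally.

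These sizes rest on three assumptions: those scored improve by the planned 2 points, actual losses match the allowance, and the unscored patients' change is as stated. The stronger reading, that the estimate is restricted to completers and inflated, is not established by the protocol. The remedy is worth making because it has to be in place before patients start to stop.

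**What to change.** In III.2 Study Procedure:

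1. **Step (3).** State that every enrolled patient who has not withdrawn consent has an IRLS at week 12, whether or not still taking the drug, and also at early stopping where possible.
2. **Step (7), and III.4 to match.** State that all these scores enter the before-after comparison. For example, the week-12 score is the second value, and the score at early stopping stands in when week 12 is missing.
3. **Step (8).** Report response and remission rates with all enrolled patients as the denominator, and say that a patient with no later score counts as a non-responder.
4. **Sensitivity analysis.** Repeat the comparison in all enrolled patients with zero change assigned to those with no later score. Zero change is a reference value, not a worst case, and should be described so.

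A mixed model and extra interim IRLS visits are optional and not needed for this repair. A model would add little for a patient who has no score after baseline.

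The cost is one short questionnaire for patients who stop, one added analysis, and an estimate that may be slightly less favourable. Section VII says that participants already attend the unit for regular dialysis, so scoring them there should need little extra effort.

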****Inclusion Criteria:****

- (1). Maintenance hemodialysis ≥ 3 months;
- (2). Age between 18-75 years;
- (3). Diagnosed with RLS according to the IRLSSG criteria and with an IRLS score > 15 points;
- (4). Willing to cooperate with this study.

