Secondary Indicators: Quality of life score (KDQOL-SF-36), Clinical Global Impression scale (CGI) score, Medical Outcomes Study Sleep Scale (MOS-SS) score, Pittsburgh Sleep Quality Index (PSQI) score, Epworth Sleepiness Scale (ESS) score, Hamilton Anxiety Rating Scale (HAMA) score, Hamilton Depression Rating Scale (HAMD) score, Self-Rating Anxiety Scale (SAS) score, Self-Rating Depression Scale (SDS) score.

Safety Indicators:

- ① Occurrence of adverse reactions: including but not limited to headache, dizziness, gastrointestinal discomfort (nausea, vomiting, abdominal pain, diarrhea), hypotension, bleeding

tendency (gingival bleeding, epistaxis, subcutaneous bruising, etc.), allergic reactions (rash, pruritus, dyspnea, etc.).

② Laboratory parameter monitoring:

* Hematological indicators: Regularly test complete blood count (including red blood cell count, hemoglobin, platelet count, etc.) and coagulation function (prothrombin time, activated partial thromboplastin time, fibrinogen, etc.) to monitor whether dipyridamole's antiplatelet aggregation effect increases bleeding risk or causes hematological abnormalities.

* Biochemical indicators: Test liver and kidney function parameters (e.g., ALT, AST, serum creatinine, blood urea nitrogen, etc.) to assess the drug's impact on liver and kidney function; monitor electrolytes (e.g., potassium, sodium, chloride, etc.) to observe if drug effects or changes in uremia condition lead to electrolyte disturbances.

③ Vital signs monitoring:

* Monitoring content: Regularly measure patients' blood pressure, heart rate, respiratory rate, body temperature, and other vital signs, with particular attention to blood pressure changes, alert for hypotension caused by the vasodilatory effect of dipyridamole.

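### The protocol names two different sets of primary outcomes, five rates in III.2(8) and the IRLS score in III.6, and never defines the response rates

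*Protocol*

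**What the plan says.** The protocol labels outcomes as primary in two places.

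- **III.2 Study Procedure, item (8):** "Primary evaluation indicators: complete remission rate, partial remission rate, overall response rate, incidence of adverse events, dropout rate". The only lead-in is "Evaluate changes in patient condition before and after treatment", with no scale, cut-off or assessment time.
- **III.6 Observation Indicators:** "Primary Indicators: Restless Legs Syndrome symptom severity score (IRLS" is the whole primary list. The secondary list holds scale scores only, with none of the five rates. Adverse reactions appear there as a safety indicator: "Occurrence of adverse reactions: including but not limited to headache".

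Three other places bear on the point.

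- **III.3 Sample Size Calculation** describes its inputs as "σ is the standard deviation of the observation indicator, reflecting data dispersion" and "Δ is the expected mean difference before and after treatment", with sigma = 4 and delta = 2. It does not name the scale.
- **III.2(7)** gives the only comparative method for rates: "Comparisons of rates before and after treatment will be performed using paired-sample chi-square tests". III.4 repeats it without the word paired.
- **Inclusion criterion (3)** is "Diagnosed with RLS according to the IRLSSG criteria and with an IRLS score > 15 points". This is the only IRLS threshold in the protocol.

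**The concern.** A reader who follows III.2(8) and a reader who follows III.6 would report different primary results from different analyses. IRLS calls for a paired t-test on a mean, and the rates would go to a chi-square test on proportions. With no ranking, IRLS or any of three overlapping response rates could be presented as primary once the scores are known. Because response has no definition, its cut-off could be chosen at the same moment.

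The test named for rates adds to the problem. Everyone enters with IRLS above 15. If response means improvement from entry, nobody can be a responder before treatment, so a before/after test compares the week-12 rate with a zero fixed by design. Adverse events on study drug and dropout have no pre-treatment value at all.

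**Working it through.** **1. The two lists side by side**

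| Outcome | III.2(8) | III.6 |
|---|---|---|
| IRLS score | not listed | primary |
| Complete remission, partial remission, overall response | primary | not listed |
| Adverse events | primary | safety (as adverse reactions) |
| Dropout | primary | not listed |

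No outcome is primary in both. The remission and response terms occur only in III.2(8).

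**2. What the sample size was built for**

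Inputs from III.3: z = 1.96 and 0.84, sigma = 4, delta = 2.

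n = [(1.96 + 0.84) × 4 / 2]² = 5.6² = 31.36, rounded up to 32. This matches the protocol.

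This is the formula for a paired mean difference. It fits a score such as IRLS. No expected or reference rate is given, so no power can be worked out for any of the five rates.

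**3. The before/after test when the baseline rate is zero**

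Take 0 of 80 responders before treatment and b after. All b discordant pairs then point the same way.

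- Exact McNemar: p = 2 × 0.5^b. For b = 5, p = 0.0625. For b = 6, p = 0.031.
- Uncorrected paired chi-square: the statistic equals b. For b = 4, p = 0.046.
- Continuity-corrected: (b − 1)²/b. For b = 6, p = 0.041.

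Significance therefore needs only 4 to 6 responders of 80 (5% to 7.5%), depending on the version of the test.

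**4. How much an open cut-off matters when there is no mean change**

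Assumptions: IRLS change is normal with mean 0, and a responder is anyone whose score falls by at least c points. The protocol states no c. SD 4 is the protocol's sigma read as the SD of change; SD 3 and SD 6 show the range. With p = P(Z ≥ c/SD), the table gives P(Binomial(80, p) ≥ 6), the chance of reaching exact McNemar p < 0.05.

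| Cut-off c | SD 3 | SD 4 | SD 6 |
|---|---|---|---|
| 4 | 75% | 99% | >99% |
| 5 | 18% | 86% | >99% |
| 6 | 1% | 45% | 99% |
| 8 | <1% | 1% | 75% |

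At SD 4 the values of p are 0.159, 0.106, 0.067 and 0.023.

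**5. Choice among outcomes alone**

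Suppose IRLS and the three response rates were each tested by a valid test at 0.05. The chance of at least one false positive is 5% if they overlap fully, 1 − 0.95⁴ = 18.5% if independent, and at most 4 × 0.05 = 20%. Adverse events and dropout are not counted. Step 3 shows that the test named for rates would not be valid for response, so this range covers only the freedom to choose among outcomes.

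**The case against.** The best defence is that III.6 governs. It is the only place that sorts outcomes into primary, secondary and safety, and the sample size agrees with it. III.2(8) is a step in a procedure list, in visibly translated English, and may only mean the main things to look at. On that reading the response rates are not primary, and their cut-offs could be left to an SAP that we have not seen. This makes III.6 the likelier intention, but the protocol does not say so, and an SAP could not remove a contradiction inside the protocol.

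A second objection is that the methods text is generic. It never says that response, adverse events or dropout will be tested before against after, and it already plans to report counts as frequencies. That is literally true. However, these are the only rates named as outcomes, and before/after is the only comparison given for rates.

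A third objection concerns the figures. The cut-offs are assumed, sigma belongs to an unnamed measure, and the cut-off results move sharply with the SD. This stands: steps 4 and 5 illustrate the problem and do not estimate it. It is also true that, on the protocol's own inputs, the paired t-test has 99% power at n = 80 and 98% at n = 64. A real effect of the assumed size would leave little need to switch outcomes. That gives no protection when there is no effect.

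Finally, the sponsor could reconcile the lists in another way, for instance with a defined response rate as primary and a sample size to match. That is open to it, but IRLS is the only choice the present sample size supports.

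**Conclusion.** The concern holds and must be fixed. The contradiction and the missing definitions are plain from the text and rest on no assumption. The sample size fits III.6 and cannot support III.2(8).

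The threshold of 4 to 6 responders of 80 assumes that response means improvement from entry and that all 80 patients are analysed. The cut-off table also assumes normal change with mean zero and the SDs shown. It establishes only that an unspecified cut-off can decide whether the test is significant when scores have not moved on average.

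Naming one primary removes the choice of outcome and cut-off. It does not remove regression to the mean or non-specific response, which remain limits of a single-arm study that selects on a high score.

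**What to change.** - **III.2(8) and III.6:** name the same single primary outcome, change in IRLS score from baseline to week 12, tested by paired t-test at two-sided 0.05.
- **III.3:** state that sigma and delta refer to IRLS change. If they came from another scale, redo the calculation.
- **Response rates:** list complete remission, partial remission and overall response as secondary. Write their definitions into the protocol before enrolment or any review of scores. Report each as a proportion with a 95% confidence interval; for example, 40/80 = 50%, exact interval 38.6% to 61.4%.
- **III.2(7) and III.4:** state that the before/after chi-square test is not used for these rates.
- **Adverse events and dropout:** list adverse-event incidence under safety and dropout rate under trial conduct.

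The cost is wording in III.2(7)–(8), III.3, III.4 and III.6, with no added visits. The sponsor gives up calling the response rates primary. No patients are added if sigma and delta hold for IRLS change. If they do not, 80 patients with complete data still give 80% power as long as sigma/delta is at most √80 / 2.8 ≈ 3.2 (normal approximation).
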